1.1 Primary Objective

To determine if autologous cells using either BMMNCs or hUCBs are safe to administer in children with CP.

Primary safety outcome measures:

- 1. In-hospital infusion toxicity: pulmonary and hepatic function; new seizures, hemorrhagic lesions or ischemic lesions on imaging.
- 2. Long-term safety: development of new mass lesions or other pathological structural changes; worsening neurological status.

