5.1.3 Baseline Visit and Bone Marrow (Placebo) Harvest/Infusion

The outpatient baseline visit will be conducted in the Pediatric Outpatient Surgery Clinic. At the baseline outpatient visit, the signed informed consent document will be reviewed with the parent(s)/LAR and assent obtained from the subjects if they are able to do so. During this 1 day outpatient visit, subjects will undergo baseline assessments including physical and neurological exams, laboratory tests, chest radiograph, oxygen saturation monitoring, psychological testing, and quality of life measurements. The neuroexam will be videotaped for blinded assessments of dystonia using standardized scales validated for use on children with CP. The research team will review information from the baseline assessments to ensure the subject remains eligible for participation and that there are no unanticipated reasons to exclude the subject, (such as recent infection). After completing the outpatient baseline visit assessments, eligible subjects will be admitted to a Children's Memorial Hermann Hospital pediatric unit.

The bone marrow harvest will be performed under sedation (Propofol) and local anesthetic before or immediately after the baseline DTMRI. The subject may be logrolled to a 45 degree angle for access to the posterior iliac crest or remain supine to access anterior iliac crest. The bone marrow harvest will be performed under aseptic conditions. The bone marrow harvest is performed using either an 11-gauge needle or 15-gauge needle inserted into the iliac crest(s). Approximately 2 – 3 mL (< 40 kg body weight) to 5 – 6 mL (> 40 kg body weight) of bone marrow aspirate will be obtained and transferred in as sterile manner in a validated Coleman® cooler at ambient temperature to the Griffin Stem Cell Laboratory (GSCL). An additional blood sample will be drawn for infectious disease testing that includes HIV 1 and II, Hepatitis B and C, HTLV 1 and II, Syphilis, CMV, West Nile Virus, and ABO blood type. Transportation, processing, assessing and quality assurance at GSCL are described in the Chemistry & Manufacturing section of the IND. Approximately 6 – 7 hours after bone marrow aspiration, subjects will receive the BMMNC via peripheral or central intravenous infusion in a time not to exceed 30 minutes. The product will be infused within 30 minutes of receipt at Children's Memorial Hermann Hospital, and will remain in the cooler until ready for infusion.

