5.1.7 Post-Infusion Period

The day following infusion will be considered Post-Infusion Day 1, regardless of what time of the day the infusion was given. Post-infusion monitoring will include hemodynamics, infusion related toxicities (pulmonary, hepatic, and renal lab indices),

and neurologic complications. Laboratory tests will include a CBC with differential, chemistry panel, hepatic function panel, and coagulation panel. As part of the pulmonary monitoring a chest x-ray will be performed and blood-oxygen saturation will be monitored by finger oximeter. In the event of pulmonary dysfunction, standard supportive therapy will be given. The research team will review the first 24 hours of post-infusion monitoring for AE/SAE's and determine if the subject is eligible for discharge home. Any serious adverse event as described in the Statistical Considerations section will be reported immediately and referred to the DSMB and evaluated for potential relationship to the protocol.

Prior to discharge, the parent(s)/LAR will be given detailed instructions regarding signs and symptoms of infection such as fever, malaise, and chills and told to check the subject's body temperature twice daily for three weeks after discharge (through postinfusion day 21). Parents(s)/LAR will be instructed to immediately report neurological changes or seizure activity to the research team. A CBC and basic chemistry panel will be obtained 21 days post-infusion (+/- 7 days). Parent(s)/LAR will be given the option of having the lab tests performed by their PCP or, for local families, here at UTHealth. The research team will have daily contact with the parent(s)/LAR through post-infusion day 21. Monitoring information will be recorded on the case report form and any reports of abnormalities will be relayed to the study PI/Co PI immediately. If indicated, the parent(s)/LAR will be instructed to have the subject seen be their PCP for further evaluation. Local families may opt to be seen by the research team for adverse events evaluation.

After discharge, the subject's PCP will be given discharge summary information. The PCP will be asked to consult with the study PI on any AE/SAE's post-infusion to ensure that appropriate therapy/treatment is given to the subject.

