5.4 Pre-Infusion Medications (All Groups)

Thirty minutes prior to the infusion, all subjects (regardless of treatment assignment) will receive intravenous Benadryl 0.5mg/Kg and Solu-Medrol 0.5mg/Kg. Additionally, the following medications will be ordered prior to the infusion and kept at the subjects' bedside: Benadryl 50 mg for injection, Epinephrine 1:10,000 – 10 mL for injection and Hydrocortisone 100 mg for injection (or Solu-Medrol 0.5mg/Kg).

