9. STATISTICAL CONSIDERATIONS

9.1 Outcomes

9.1.1 Primary Safety Objective

Baseline characteristics of participants will be summarized using descriptive statistics and tabulations. Evaluation of data will be guided by exploratory analyses. All results will be reported as point estimates (percentages for binary outcomes and means \pm SD and median (range) for continuous outcomes) with corresponding interval estimates (two-sided 95% confidence intervals). No adjustments for multiple comparisons will be made and a p-value of 0.05 will be considered statistically significant.

These data are collected over time and will be longitudinal in nature with several predefined points of follow-up. We will use analytic strategies and methods applicable to such designs. For each participant in the cohort we have a set of "k" independent variables $\mathbf{x}' = (x_1, x_2, ..., x_k)$, of which some may be time varying (e.g., blood pressure) and others do not change over time (e.g., gender). In addition, the outcome variables of interest are also measured repeatedly over time (e.g., temperature, signs of infection, neurological exams, CBC, chem-20). We plan to explore any changes over time between hospital discharge and long-term follow-up at 6 months, 1 year, and 2 years after cell treatment with repeated measure model analyses. In this study, we plan to explore and identify potential factors associated with time to SAEs, AEs, death (refer to section 6.2), loss to follow-up (short term and long term), and improvements in functional outcomes (refer to section 6.3). We plan to explore the factors associated with the time to an event using survival analysis methods which incorporate information about the timing of withdrawals, deaths, and functional improvements (if any) of subjects during the follow up period. We plan to first use descriptive statistics to explore the characteristics of the subjects among events and then will use the Kaplan-Meier method to estimate the time to an event. Combined, these secondary analyses may provide useful preliminary estimates for the design of future cell studies.

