14. APPENDIX A

Bone Marrow Group:

												1
Study Procedures	Screening Period	Baseline Clinic Visit	Admission to MHH	Study Day 1 (Post-Infusion)	Study Day 2-21 (Post-Infusion)	* 6-Month Follow-Up Clinic Visit	* 1-Year Follow-Up Clinic Visit	* 1-Year Crossover Group Clinic Visit	Crossover Group Admission to MHH	Crossover Group Study Day 1 (Post-Infusion)	Crossover Group Study Days 2 - 21 (Post-Infusion)	* 2-Year End of Study Clinic Visit
Review of Medical Records	Х	х						х				
Consent		¹ X	9 3					Х				
Randomization		х									2	
History	Х	х				х	Х	Х				х
Physical		х	X	х		х	Х	Х	х	Х		х
Videotaped Motor/Cognitive Evaluation		х				х	х	х				х
Vital Signs		х	X	х	х	х	Х	Х	х	Х	Х	х
Infectious Disease Tests			² X									
Lab Evaluation		³ X	3X	3X	⁴ x	³ X	³ X	³ X	³ X	³ X	⁴ x	³ X
Chest X-Ray			х	х		х	Х		х	х		х
DT-MRI			Х				Х		Х		5	х
Bone Marrow / Sham Harvest			Х						⁶ x			
Stem Cell or Placebo Infusion			х						⁶ X			
Neuropsych Evaluation		х				×	x	x				х
Hospital Discharge				⁵ X						⁵ x		
Post-Infusion Safety Monitoring					х						х	
Evaluation for AE/SAEs		х	x	х	х	х	×	X	х	x	x	x

^{*} The 6 month return visit window is +/- 14 days from infusion and +/- 21 days for the 1 and 2 year return visits.

¹ The informed consent document will be sent to the family/LAR during the screening period and reviewed by conference call before the baseline visit.

². Infectious Disease Tests include HIV, Hepatitis, Syphilis, and West Nile Virus.

³ Lab tests include CBC with Differential and Platelets, and Comprehensive Metabolic/Coagulation Panels.

⁴ Post-infusion CBC and basic chemistry pannel on day 21 (+/- 7 days).

⁵ Subjects will receive 24 hours of monitoring post-infusion before discharge.

⁶. Placebo Crossover to BMMNC harvest and stem cell infusion.

Cord Blood Group:

Study Procedures	Screening Period	6 - 8 Weeks Before Visit	Baseline Clinic Visit	Admission to MHH	Study Day 1 (Post-Infusion)	Study Days 2 - 21 (Post-Infusion)	• 6-Month Follow-Up Clinic Visit	+ 1-Year Follow-Up Clinic Visit	* 1-Year Crossover Group Clinic Visit	Crossover Group Admission to MHH	Crossover Group Study Day 1 (Post-Infusion)	Crossover Group Study Days 2 - 21 (Post-Infusion)	* 2-Year End of Study Clinic Visit
Review of Medical Recods	х												
Consent			¹ x					Х	x				x
History			Х										8
Physical			х	Х	Х		Х	Х	Х	Х	Х		х
Infectious Disease and HLA Tests		²x							х				
CBR Release of Cord Blood Tests		³ X							х				
Randomization	1	⁴ x		6. F.									8

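### The exploratory safety model in section 9.1.1 starts at hospital discharge, so an infusion-related shift too small to be reported as an event shows as no change if it lasts and as improvement if it resolves

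*Combined protocol and SAP*

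**What the plan says.** Under the primary safety objective, section 9.1.1 says that "the outcome variables of interest are also measured repeatedly over time (e.g., temperature, signs of infection, neurological exams, CBC, chem-20" and plans repeated-measures analyses to "explore any changes over time between hospital discharge and long-term follow-up at 6 months, 1 year, and 2 years after cell treatment". Baseline enters that section only as a descriptive summary of participant characteristics.

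The first primary safety outcome in section 1.1 is "In-hospital infusion toxicity: pulmonary and hepatic function; new seizures, hemorrhagic lesions or ischemic lesions on imaging". The second is long-term safety, including worsening neurological status.

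On timing, Appendix A states that "Subjects will receive 24 hours of monitoring post-infusion before discharge". Sections 5.1.7 and 5.2.9 place laboratory work in this post-infusion period: "Laboratory tests will include a CBC with differential, chemistry panel, hepatic function panel, and coagulation panel".

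Before infusion, at the outpatient baseline visit, "subjects will undergo baseline assessments including physical and neurological exams, laboratory tests, chest radiograph". Section 5.2.7 says the same for the cord blood arm, and both tables in Appendix A schedule laboratory tests at that visit.

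The imaging model in section 9.1.2 does start at baseline, followed by 1 and 2 years.

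**The concern.** The first time point named for the safety model is already post-treatment. By then the child has had the infusion, the pre-medication ("all subjects (regardless of treatment assignment) will receive intravenous Benadryl 0.5mg/Kg and Solu-Medrol 0.5mg/Kg"), intravenous fluid and, in the marrow arm, a harvest or sham harvest under sedation. Change measured from there cannot show what happened between the baseline visit and discharge.

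What is at stake is a moderate shift in a continuous value that is too small to be recorded as an adverse event or to reach a stopping threshold. A group-level model is the natural tool for finding such a shift, and this is the only longitudinal model planned for safety values. Started at discharge, it would report a lasting shift as stability and a transient one as improvement after cells. Section 9.1.1 intends its estimates to inform the design of future cell studies, so the error could be carried forward.

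**Working it through.** The documents give no effect size, SD or power for this model, so there is no stated figure to reproduce. The check is a comparison of sections, then algebra, then an illustration.

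**1. Time points available and time points used**

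| Time point | Collected? | In the 9.1.1 safety model? |
|---|---|---|
| Baseline clinic visit, before infusion | Yes, both arms (5.1.3, 5.2.7, Appendix A) | Not named |
| Admission | Yes, but the same Appendix A column contains the infusion, so it is not shown that the sample precedes it | Not named |
| Day 1 / discharge | Yes | First point named |
| Day 21 | CBC and basic chemistry only | Not named separately |
| 6 months, 1 year, 2 years | Yes | Named |

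The videotaped motor/cognitive evaluation is scheduled at baseline and the follow-up visits but not at discharge. For that measure the model has no starting value at all.

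**2. Algebra**

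Let infusion shift the treated group's mean by d at discharge, with a fraction f remaining at follow-up, and let sham show no shift.

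- From baseline: fd - 0 = fd.
- From discharge: fd - d = (f-1)d.

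| f | From baseline | From discharge |
|---|---|---|
| 1 (persists) | d | 0 |
| 0.5 | 0.5d | -0.5d |
| 0 (resolves) | 0 | -d |

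This holds whatever the size of d.

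**3. Illustration of size**

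From the documents: 30 children randomised 2:1 (section 3), so 30 x 2/3 = 20 treated and 30 x 1/3 = 10 sham; significance at 0.05 with no multiplicity adjustment (9.1.1).

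Assumed, not in the documents: d from 0.5 to 1.5 SD; equal correlation rho between time points of 0.5 or 0.7; a two-sided t-test of treated against sham on change to 6 months, which precedes any crossover; complete data.

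The SD of a change is sqrt(2(1-rho)): 1.00 at rho = 0.5 and 0.77 at rho = 0.7. The standard error of the contrast is that SD times sqrt(1/20 + 1/10) = 0.387, giving 0.387 and 0.300.

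Rejection rates for a fully persistent shift, 20,000 simulated trials per setting (ranges run from rho 0.5 to 0.7):

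| d | From baseline | From discharge |
|---|---|---|
| 0.5 SD | 23-36% | about 5% |
| 1.0 SD | 70-89% | about 5% |
| 1.5 SD | 96-99.7% | about 5% |

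The normal approximation gives 73% and 92% at d = 1.0, in reasonable agreement. For a fully resolved shift the pattern reverses. At d = 1.0 the discharge-based test rejects in the direction of improvement in 70-89% of trials, and the baseline-based test stays at 5%.

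**The case against.** **Acute harm is assessed elsewhere.** This stands. Section 9.1.1 itself plans time-to-event analysis of AEs and SAEs with reference to section 6.2. Section 6.2 defines events against baseline or absolute thresholds, chest films are compared between baseline and Day 1, AEs are collected from randomisation (10.7), and the stopping rules (10.8.1) include AST/ALT above 900 within 24 hours. What these do not supply is a group-level estimate of shifts below such thresholds.

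**The analysis is exploratory.** This also stands. Section 9.1.1 speaks of exploring changes and closes by calling these analyses secondary; its general reporting is point estimates with 95% intervals. A reader might infer that the primary safety analysis hides toxicity. The documents do not support that: this is one exploratory model beside event-based reporting, although it sits under the primary safety heading.

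**The window may be meant for long-term safety only.** This is plausible, because section 1.1 separates in-hospital from long-term outcomes. But a lasting change caused by infusion is itself a long-term safety matter, and it is the case that the window misses.

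**Discharge is never called the reference, and the unspecified covariates could include baseline.** This is true, but the text does not say that they do. If a group term were fitted, a lasting shift could also appear as a constant difference between groups. Section 9.1.1 names no such term, and without baseline that difference cannot be separated from chance imbalance between 20 and 10 children.

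**Shared peri-infusion care.** A reader might infer that pre-medication alone would often produce false significance in a pooled test of all 30 children. The documents give no size for such a disturbance, and pre-medication goes to every child, so it would largely cancel in a treated-versus-sham contrast. The point does not rest on it.

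**Conclusion.** The point holds as a limited one. As written, the longitudinal safety model measures change from a post-infusion value and leaves out a pre-infusion value that both arms already collect. The direction of the error follows from the algebra alone: lasting shifts go to zero and resolved shifts look like improvement.

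The size depends on assumptions that the documents do not supply. At a lasting shift of 1.0 SD, the illustration gives detection of 70-89% from baseline against the nominal 5% from discharge. At 0.5 SD even the baseline-based analysis detects only 23-36%, so the repair removes the distortion without making the trial sensitive to small shifts.

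The exposure is confined to changes below the AE and stopping thresholds in an exploratory analysis. It is worth correcting before the data are analysed, but it does not undermine the trial's main safety reporting.

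**What to change.** In section 9.1.1:

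- Make the baseline clinic visit value the reference for each longitudinal safety variable, either as the first time point or as a covariate. Use an admission value only where it is documented as taken before infusion.
- Keep Day 1/discharge, day 21 (CBC and basic chemistry only), 6 months, 1 year and 2 years as post-infusion time points.
- Report the baseline-to-Day-1 change by treatment group.
- For sham children who cross over, use the original baseline for the randomised comparison up to the crossover infusion. For data after their cell infusion, use the 1-year crossover clinic value, which Appendix A already schedules.

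The discharge-to-follow-up contrast can still be reported from the same model. No visit, test or child is added, and the cost is a few sentences and a small amount of extra analysis work.

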1.2 Secondary Objective

To determine if late functional outcomes are improved following the administration of autologous cells compared with subjects in the control group. Efficacy outcome measures:

- 1. aMRI volumetric white matter, grey matter, and CSF space volumes at Baseline, 1 year and 2 years post-treatment. Detailed volumetric analysis of the corpus callosum and white matter tract such as the corticospinal tract will be measured (fractional anisotropy and mean diffusivity) as well. Specific white matter tract analysis will be identified at baseline MRI and correlated with motor function studies as the primary lesion of interest. Total volumes and specific tract lesions will be analyzed and correlated with functional outcomes.
- 2. The following functional outcomes studies will be performed at baseline, 6 months, 1 year after infusion, and 2 year after infusion.
 - a. Gross Motor Function Measures
 - b. Psychological Assessment Batteries

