6.3 Psychological & Functional Outcome Assessment Tests

The following tests will be performed at baseline and all follow-up visits for children who have the visual, motor, and language abilities needed to complete the assessment tasks, (note table in Appendix B).

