6.3.1 Motor Functioning

The Gross Motor Fine Motor - 88 Scale (GMFM-88) is an 88-item standardized, observation-based assessment of children's gross and fine motor abilities. It was designed for motor assessment of children with cerebral palsy. Administration time is 45-60 minutes.

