8.2 Withdrawal of Individual Subjects

The Principal Investigator will make every reasonable effort to keep each subject in the study through the 2 year visit. If a subject withdraws from the study, the reason for withdrawal must be documented in the study chart. Possible reasons for withdrawal include: adverse experiences, protocol deviation, including non-compliance, lost to follow-up, discretion of investigator or DSMB, or other regulatory agency/body. Subjects will be withdrawn from the study immediately if any of the following occur:

- a. The subject or their parent(s)/LAR requests withdrawal from the study.
- b. The investigator believes it is in the best interest of the subject.
- c. There is clinically significant deterioration of the subject's medical status that warrants termination from the study.
- d. There are clinically significant abnormal laboratory results that warrant termination from the study.

[figure not shown]

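### Section 9.1.1 treats improvement on repeated functional scores as an undefined Kaplan-Meier event, so the curve accumulates chance rises and overstates absolute improvement in both randomised groups

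*Combined protocol and SAP*

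**What the plan says.** Section 9.1.1 lists the outcomes whose time to occurrence will be explored. After serious adverse events, adverse events and death it adds "loss to follow-up (short term and long term), and improvements in functional outcomes (refer to section 6.3". The methods are "survival analysis methods which incorporate information about the timing of withdrawals, deaths, and functional improvements (if any) of subjects", and after a descriptive step the investigators "will use the Kaplan-Meier method to estimate the time to an event". The stated use is modest: "Combined, these secondary analyses may provide useful preliminary estimates for the design of future cell studies".

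The outcomes themselves are scores. Section 6.3 says "The following tests will be performed at baseline and all follow-up visits for children who have the visual, motor, and language abilities needed". The motor measure, GMFM-88, "is an 88-item standardized, observation-based assessment of children's gross and fine motor abilities"; the others include VABS-2, MVPT-3, NEPSY-II Narrative Memory, PPVT-4 and EVT-2. On timing, section 1.2 says "The following functional outcomes studies will be performed at baseline, 6 months, 1 year after infusion, and 2 year after infusion".

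Neither section 6.3 nor section 9 says which instrument defines an improvement, how large a gain must be, how measurement error is allowed for, whether a gain must be confirmed, or what happens if it is later lost. No reliability, SD or SEM is given for any instrument.

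**The concern.** Death or a serious adverse event happens once and at a known time. A test score does neither. It is re-measured at three follow-up visits, it can go up and down, and part of each change is measurement error. If improvement becomes an event, a child counts as improved from the first qualifying visit onward, so a later fall does not lower the curve. Each further visit gives an unchanged child another chance to qualify by luck. Since events can be recorded only at three visits, the curve also says little about timing beyond what the visit-by-visit results already show.

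Two things are at stake. First, the curve would be read as the share of children who improved after cell treatment and carried into the planning of a later trial. Second, reducing a score to a yes/no event discards information in a trial of 30 children. This matters more because section 9.1.2 has no plain comparison of the functional scores by group. Its repeated-measures model is for imaging variables, and function enters through correlations with imaging or through models that also contain MRI/DTI variables. Yet section 1.2 makes better late function than in the control group the secondary objective.

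**Working it through.** The plan gives no figure for this analysis, so there is none to reproduce.

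**Inputs from the documents:** one baseline and k = 1, 2, 3 follow-up assessments at 6 months, 1 year and 2 years (section 1.2); Kaplan-Meier on time to improvement (section 9.1.1).

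**Assumptions:** one continuous score; no true change; independent, identically distributed measurement error at each visit; improved means exceeding baseline by more than c at any visit so far, with c in SEM units. The documents supply neither c nor the SEM, so a range is shown.

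**Any rise counts (c = 0).** A child is not counted only if baseline is the highest of k + 1 exchangeable values, which has probability 1/(k + 1). The share counted as improved is therefore k/(k + 1): 1/2 = 50%, 2/3 = 66.7%, 3/4 = 75%. This holds for any continuous error distribution and any SD.

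**With a threshold.** For normal errors, let B be the baseline error in SEM units. The share improved by visit k is 1 − E[Φ(B + c)^k]. The share at any single visit is 1 − Φ(c/√2), the same at each visit. By numerical integration:

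| Threshold c (SEM) | By 6 months (= single visit) | By 1 year | By 2 years | 2-year ÷ single visit |
|---|---|---|---|---|
| 0 | 50.0% | 66.7% | 75.0% | 1.5 |
| 0.5 | 36.2% | 51.7% | 60.7% | 1.7 |
| 1 | 24.0% | 36.6% | 44.8% | 1.9 |
| 1.5 | 14.4% | 23.4% | 29.8% | 2.1 |
| 2.33 | 5.0% | 8.8% | 11.8% | 2.4 |
| 2.77 | 2.5% | 4.5% | 6.3% | 2.5 |

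The last two thresholds are 1.645 × √2 and 1.96 × √2 SEM, which give single-visit false-positive rates of 5% and 2.5%.

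**Confirmation at the next scheduled visit** (simulation, 2 million children): the 2-year share falls from 75% to 41.6% at c = 0, from 44.8% to 15.8% at 1 SEM, from 11.8% to 1.9% at 2.33 SEM and from 6.3% to 0.8% at 2.77 SEM.

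**Serially correlated error.** With correlation over one year of 0.3 to 0.9 and no threshold, the 2-year share is 74% to 71%, so independence is not what drives the result.

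**By group.** Randomisation is 2:1 in 30 children, so 30 × 2/3 = 20 treated and 30 × 1/3 = 10 sham. At 1 SEM the expected chance improvers by 2 years are 0.448 × 20 = 9.0 and 0.448 × 10 = 4.5: the same share in each group.

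**The case against.** The strongest reply is that the protocol never says any rise counts. That is right. The 75% is an upper limit for one score without true change; tied scores lower it, and a strict threshold with confirmation brings it below 1%. A reader might infer that three quarters of unchanged children will be declared improved. The documents do not support that, because they state no rule at all. What stands is that the share grows from visit to visit at every threshold shown.

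A reader might also infer a false treatment effect. This does not follow, since chance rises occur in both randomised groups. Section 5.1.8 has the blind broken before the 1-year visit, so expectation could act differently by group from then on, but that is a separate matter from the choice of Kaplan-Meier.

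A third tempting reading is that withdrawal biases the curve upward, because section 8.2 withdraws a child when "There is clinically significant deterioration of the subject's medical status that warrants termination from the study" and Kaplan-Meier would censor that child. This is weak. The criterion concerns medical status, not functional scores, and sections 8.3 and 8.4 ask withdrawn children to continue scheduled evaluations and complete an end-of-study evaluation. There is no basis for counting them as not improved by rule.

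On power, simulations of 20 v 10 children with visits at 6 months and 1 year favour a baseline-adjusted mean score over a log-rank test of first improvement: about 73% against 36–50% for an assumed effect of 1.25 SEM. The gap depends on the inputs: 17% against 4–12% at 0.5 SEM, 100% against 96–100% at 3 SEM, and 37% against 22–26% at 1.25 SEM when true change varies between children with SD 1.5 SEM. The documents name no log-rank test, so only the direction is relied on here.

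Finally, these analyses are exploratory, and section 9.1.1 also mentions repeated-measures models over the follow-up visits. Its examples there are safety variables such as temperature and blood counts, so it does not clearly cover the functional scores. Defining the event in advance would indeed cure most of the inflation, but that too requires changing the text.

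**Conclusion.** The point holds in a limited form. Kaplan-Meier on improvement is a poor fit to scores taken at three follow-up visits with no defined event. With no true change, the 2-year share counted as improved on one score lies between about 6% (2.77 SEM threshold) and an upper limit of 75% (any rise), or about 1.5 to 2.5 times the single-visit share over that range. These figures assume exchangeable measurement error and no confirmation; where this trial would fall cannot be said, because the documents give neither threshold nor SEM. The consequence is inflated absolute improvement estimates for planning and a loss of information of uncertain size. The analysis is exploratory, which limits its weight, but a better method is available at almost no cost and section 9.1.2 leaves a gap for it to fill.

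**What to change.** In section 9.1.1, remove functional improvement from the outcomes for survival methods and Kaplan-Meier. In section 9.1.2, state that each section 6.3 score will be analysed as a continuous value, adjusted for its baseline, by randomised group at 6 months and 1 year. Note that the 1-year assessment follows unblinding, and label the 2-year results as following both unblinding and possible cross-over.

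If a responder figure is wanted, name the instrument, set in advance a threshold larger than its measurement error, with the source of the SEM, and report the proportion above it at each visit by randomised group. Alternatively, require confirmation at the next visit, accepting that a gain first seen at 2 years cannot be confirmed. Either way, use any scores collected after withdrawal under section 8.4.

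The cost is wording only, with no new data; a responder definition would also need a sourced SEM for the chosen instrument. The downside is that there is no time-to-improvement curve, and the reported improvement figures will be lower.
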